## **3.3** Computing Environment

All descriptive and statistical analyses will be performed using SAS statistical software Version 9.4, or later version. Medical history and AEs will be coded using the Medical Dictionary for Regulatory Activities (MedDRA), Version 24.0. Concomitant medications will be coded using the World Health Organization Drug Dictionary (WHO DRUG DDE+HD/2017-DEC-B3).

## 3.4 **Baseline Definitions**

The baseline value is defined as the last non-missing value obtained prior to the first dose of study medication, including the screening value, if necessary. If a randomized subject is not treated, the baseline value is defined as the last non-missing assessment.

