4.3.2. Handling of Participant Withdrawals or Terminations

If a subject is withdrawn or discontinued from the study, the reason for withdrawal from the study is to be recorded in the source documents and on the CRF. All subjects withdrawn prior to completing the study should be encouraged to complete study procedures scheduled for the Month 12/Early Termination visit as soon as possible, and to return in 1 month for a Follow-up Visit. All AEs should be followed as described in Section 7. Subjects who discontinue or are withdrawn from the study will not be replaced.

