- 9. Serum calcium and albumin will be measured predose from the standard chemistry panel on Month 1 and Month 6, and from a separate blood draw at Day 1, Month 3 and Month 9 and 4 hours post dose at Day 1, Month 1, Month 3, Month 6, and Month 9.
- 10. A 24-hour urine collection will be collected at Day 1 and Month 3 and will be used for urinary calcium and urinary creatinine measurements. Subjects will discard the first void and begin a 24-hour urine collection on the day prior to the clinic visit.
- 11. If the subject reports that a fracture has occurred, remind the subject to bring X-rays and any medical reports of the fracture to the next clinic visit. Documentation must be obtained on all new fractures that occur during the study. This documentation should be maintained in the source documents.
- 12. Each DXA for a given subject should be performed on the same machine, and if available, preferably by the same technician. For screening purposes, DXA scans of the lumbar spine, total hip, and femoral neck taken up to 35 days prior to the beginning of the Screening Period, with a study-approved scanner, may be used to determine study eligibility.
- 13. The first wrist DXA will be performed prior to study drug administration on Day 1 and should be performed on the same machine, and if available, preferably by the same technician.
- 14. QCT performed in a subset of subjects at selected study sites.
- 15. Samples will be drawn prior to treatment on Day 1, Months 1, 3, 6, 9, and 12, and the Follow-up Visit scheduled at 1 month after the last dose of study medication.
- 16. The subject will maintain a diary of their assessment of local tolerance beginning on Day 2 and continuing through Day 7 in Month 1, and beginning on Day 2 and continuing through Day 7 in Month 9.
- 17. The subject medication diary will be reviewed by study personnel at each study visit to ensure subject compliance.
- 18. AEs and SAEs will be recorded on the case report forms starting from the time of subject entry into the Screening Period (Visit 1) of the study (signed informed consent) until 30 days after the last dose of study medication. All AEs will be followed until resolution or stabilization. Any SAEs that occur at any time after completion of the study, which are considered by the Investigator to be related to study treatment, must be reported to the Sponsor or its designee.

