8.4. Description of Statistical Methods

8.4.1. General Approach

Analyses will be presented by treatment group (abaloparatide-SC and placebo) and overall, when appropriate. Baseline is defined as the last value obtained prior to the first dose of study medication.

For categorical data, summary tabulations of the number and percentage of subjects within each category of the parameter will be presented. For continuous data, the number of subjects, mean, median, standard deviation (SD), minimum, interquartile range (Q1 and Q3), and maximum will be presented.

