#### Intention-to-treat (ITT) population

The Intention-to-Treat (ITT) population is defined as all subjects randomized into this study.

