#### 3.12 Visit Windows

In general, the nominal visit will be used for the safety and efficacy data summaries and analyses.

During the COVID-19 pandemic, if a subject's DXA and/or QCT assessment cannot be performed during the protocol specified visit windows, the site will contact the study Medical Monitor and the subject will be allowed to make up the visits within an allowed time period. The allowable time period for collection of DXA and QCT assessments are shown in Table 3, where the ideal visit date is defined as the date that represents the ideal number of days from the date of first dose of study drug to the nominal visit.

Table 3:         Allowable Time Period for Collection of DXA and QCT Assessment
---

Visit	Ideal Visit Day	BMD or vBMD Assessment
Month 3	90	Up to 30 days after ideal visit day
Month 6	180	Up to 90 days after ideal visit day
Month 12	360	Up to 30 days after ideal visit day

Due to the expanded time periods for collection of efficacy assessments, analysis visit windows are defined below for the analyses of BMD, vBMD, and serum markers of bone metabolism (PINP and CTX) data to determine the assessment that will be used for a given study visit.

Table 4: Analysis V	Visit Windows	for BMD.	, vBMD, s	s-PINP and	I s-CTX.
---------------------	---------------	----------	-----------	------------	----------

Visit / Month	Allowable days from first dose of study drug			
	BMD lumbar spine, total hip and femoral neck, BMD Wrist	s-PINP, s-CTX	vBMD	
Visit 3 / Baseline	≤1	$\leq 1$	≤ 1	
Visit 4 / Month 1		2—60		
Visit 5 / Month 3	2—120	61—120		
Visit 6 / Month 6	121—270	121—270		
Visit 7 / Month 9				
Visit 8 / Month 12	≥ 271	≥271	≥2	

*Study BA058-05-019 SAP* 

It is possible that more than 1 assessment for a parameter may be obtained within the same analysis visit window. In such circumstances, the assessment with the date closest to the ideal visit day will be used. In the event that 2 assessments are equidistant to the ideal visit day, the later of the assessments will be used.

The analysis visit window convention will not be applied to the data listings. The data listings will display all data as collected with the corresponding nominal visit.

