## 4.3 Efficacy Analyses

The ITT population will be the primary population for all efficacy analyses. The PP population will be used for supportive analyses. In efficacy analyses, subjects will be analyzed according to the treatment to which they were randomized.

The primary and BMD-related secondary efficacy endpoints will be derived from the Bioclinicacorrected BMD measurements.

BMD scans may be deemed unevaluable at the first reading and a repeat BMD scan may be performed. The re-scan BMD assessment will be recorded as an unscheduled visit for the corresponding nominal visit. To determine the assessment that will be used for a given study visit by the analysis window convention, all BMD assessments (including unscheduled BMD assessments) will be considered. In the efficacy analyses by nominal visit, unscheduled BMD assessments will be used if the BMD assessment at the nominal visit is not available but an unscheduled BMD assessment for the same nominal visit is available.

Analyses of the BMD-related efficacy endpoints and the serum markers of bone metabolism (s-PINP and s-CTX) will be conducted using the analysis visit windows defined in Table 4 of Section 3.12 as the primary analysis. Analyses of the BMD-related efficacy endpoints and the serum markers of bone metabolism (s-PINP and s-CTX) using the nominal visits will also be presented as supportive analyses.

All confidence intervals, statistical tests, and p-values will be reported as nominal 2-sided. The primary and key secondary efficacy endpoints will be assessed at the significance level of 0.01. All other efficacy endpoints will be assessed at a significance level of 0.05.

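### For randomised but undosed men, SAP 3.4 sets baseline with no cut at randomisation, so an Early Termination scan can become the baseline

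*SAP*

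**What the plan says.** **Who is analysed.** SAP 2.1: "The Intention-to-Treat (ITT) population is defined as all subjects randomized into this study". SAP 4.3 makes this the primary population for all efficacy analyses, so a man randomised but never dosed is included.

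**Baseline.** For treated men, SAP 3.4 uses the "last non-missing value obtained prior to the first dose of study medication, including the screening value, if necessary". For the others: "If a randomized subject is not treated, the baseline value is defined as the last non-missing assessment". Protocol 8.4.1 has only the pre-dose rule ("Baseline is defined as the last value obtained prior to the first dose of study medication") and does not cover undosed men.

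**Where a later scan could come from.** Under Protocol 4.3.2, subjects withdrawn early "should be encouraged to complete study procedures scheduled for the Month 12/Early Termination visit as soon as possible". Protocol 6.2.13 puts DXA of the lumbar spine, total hip, femoral neck and wrist at that visit.

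**How scans are placed.** The column heading of SAP Table 4 is "Allowable days from first dose of study drug". Baseline is day 1 or earlier, Month 3 is days 2 to 120, Month 6 is days 121 to 270, and Month 12 is day 271 onward. Table 5, for the COVID-19 sensitivity analyses, also counts from first dose.

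**Re-scans.** SAP 4.3 covers the repeat of an unevaluable scan: "The re-scan BMD assessment will be recorded as an unscheduled visit for the corresponding nominal visit". In the windowed main analysis all such scans go through the window allocation. In the supportive nominal-visit analysis, a re-scan may stand in for an unavailable scan at its visit.

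**The concern.** The treated-man rule has a cut-off and the untreated-man rule has none. The only post-randomisation DXA an undosed man is likely to have is the one at Early Termination. As written, that scan is his last non-missing assessment and therefore his baseline at every skeletal site. A measured outcome is turned into a reference value, and the true pre-randomisation scan is set aside.

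Baseline has three roles in the primary analysis: predictor in the imputation, denominator of the percent change, and ANCOVA covariate. An error in it reaches the primary and key secondary endpoints. The window tables do not correct it, because a man with no first dose has no day count.

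**Working it through.** There is no stated figure to reproduce. The check applies the rules to one man and then bounds the effect.

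**1. One undosed man, illustrative values.** Assume lumbar spine BMD is 0.80 at screening and 0.79 at Early Termination, 30 days after randomisation.

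| | SAP 3.4 read literally | Baseline limited to randomisation or earlier, randomisation date = Day 1 |
|---|---|---|
| Baseline | 0.79 | 0.80 |
| Place of the later scan | used up as baseline; no day count for Table 4 | Month 3 (day 30 lies in 2 to 120) |
| Observed change | none available | (0.79 − 0.80)/0.80 = −1.25% |
| LOCF change at Month 12 | (0.79 − 0.79)/0.79 = 0% | −1.25% |
| MMRM | no post-baseline value | contributes a Month 3 value |
| Month 12 in the primary analysis | imputed, conditioning on 0.79 | imputed, conditioning on 0.80 |

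The LOCF zero arises because SAP 4.3.1 lets the carried value be the baseline itself. With the last scan as baseline, there is nothing later to carry.

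**2. What the correction recovers at Month 12.** The Month 12 window opens at day 271. An Early Termination visit held promptly after randomisation falls well short of that, so Month 12 normally stays missing under either rule. In the abaloparatide arm, step 3 of SAP 4.3.1 imputes it from baseline and placebo data, so an interim scan there adds nothing beyond the corrected baseline. In the placebo arm the interim value can feed the sequential regression. In both arms it counts in the Month 3 or 6 analyses, MMRM and LOCF.

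**3. Size.** The documents give no count of undosed men. If 0% to 2% of 225 are never dosed (an assumption), that is 0 to 225 × 0.02 = 4.5, so at most 4 men. Only those who also return for a DXA matter. On the illustrative −1.25%, one such man shifts the unadjusted LOCF mean of his arm by:
- placebo: 1.25/75 = 0.017 percentage points;
- abaloparatide: 1.25/150 = 0.008 percentage points.

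Four men, all on placebo, would give 4 × 1.25/75 = 0.067 points, against a planning difference of 6.5. The effect on the primary estimate runs through the imputation model and cannot be computed from the documents.

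**4. Wrist re-scan in a dosed man.** Protocol Table 3, footnote 13: "The first wrist DXA will be performed prior to study drug administration on Day 1". No wrist scan is scheduled at screening. A re-scan on day 2 or later is not pre-dose and falls in the Month 3 window. The scan closest to day 90 is used: re-scans on days 2, 7, 14 and 30 lie 88, 83, 76 and 60 days away, while a regular scan on days 86 to 120 is at most 30 days away and wins. The open question is whether the nominal-visit substitution in SAP 4.3 makes the re-scan a Day 1 value despite the pre-dose definition in SAP 3.4.

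**The case against.** The intent is presumably the last value before randomisation, and a sensible programmer might code it that way. But the SAP sentence says otherwise, and the adjacent sentence shows that its authors write a cut-off when they want one.

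The group is tiny. Randomisation and the first in-clinic dose are both at Visit 3, and Protocol 9.9 promises a completed eCRF only for dosed subjects, so an undosed man's later scan might never be recorded. The small size stands. The eCRF point does not remove the problem, because SAP 3.4 itself provides for untreated men.

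Month 12 would usually be imputed either way. This stands, and it limits the benefit to a correct baseline plus retained interim data.

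A reader might infer that the rule breaches the intention-to-treat principle. The documents do not support that: these men stay in the ITT population and are analysed in the arm to which they were randomised. The fault is a wrong reference value, not a changed population or assignment.

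**Conclusion.** The rule is wrong as written and its impact is small. It requires a man who is randomised, not dosed, and scanned after randomisation; how many there will be is unknown and probably very few. For such a man it gives a post-randomisation baseline at all sites, discards his observed change and forces zero change under LOCF. It touches the primary ITT analysis, but nothing suggests that it could alter the trial's conclusion.

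A reader might go further and infer that dosed men with an unevaluable Day 1 wrist scan wrongly lose their wrist endpoints, and that a post-dose re-scan should serve as baseline. The documents do not support this. Protocol 8.4.1 and SAP 3.4 both require a pre-dose value, so refusing the re-scan follows the plan. Reading turnaround is not stated, and a repeat before dosing on Day 1 would be valid. Exclusion for a missing baseline is written only for LOCF, not for the main imputation analysis. Mislabelling as Month 3 is nearly ruled out by the closest-to-day-90 rule. What remains is a narrow inconsistency between SAP 3.4 and SAP 4.3, confined to additional secondary endpoints outside the fixed sequence; spine and hip baselines come from screening.

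**What to change.** 1. In SAP 3.4, replace the second sentence with: *for randomised subjects not treated, baseline is the last non-missing assessment on or before the date of randomisation.*
2. In SAP 3.12 and 4.3.1, state that for these men the randomisation date is Day 1 for Tables 4 and 5 and for the ideal visit days.
3. State which rule governs a Day 1 wrist re-scan taken after dosing, reconciling the substitution rule in SAP 4.3 with the pre-dose definition in SAP 3.4, so that the windowed and nominal-visit analyses treat it alike. Keeping the pre-dose definition needs only a statement that wrist baseline is then missing in both.

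The cost is SAP wording and a few lines of programming, with no new data, visits or subjects. It should be done before unblinding, so that nobody has to choose a baseline scan with treatment known. One consequence to accept is that an undosed man with no wrist scan by the date of randomisation will have no wrist baseline.

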## 3.5 Data Pooling

Data from all study sites and countries will be pooled together for all analyses, unless otherwise specified.

## 3.6 Adjustments for Covariates

Adjustments for covariates will be employed in the Analysis of Covariance (ANCOVA) and Mixed-Effect Model for Repeated Measures (MMRM) analyses. Any adjustments will be prespecified in the description of the statistical analysis (Section 4).

# **3.7** Fixed-Sequence Tests of the Primary and Key Secondary Efficacy Endpoints for Multiple Comparisons

The primary and key secondary efficacy endpoints will be analyzed using a fixed-sequence testing procedure to control the family-wise error rate for any joint distribution of hypothesis test statistics. To claim statistical significance at the 2-sided level of 1%, the following 3 fixed-sequence tests will be performed in sequential order. At any step of the sequential testing, if the treatment difference is not statistically significant at the 1% level then all the subsequent comparisons following the fixed sequence cannot be claimed statistically significant.

- 1. Percent change from baseline in BMD at the lumbar spine at 12 months
- 2. Percent change from baseline in BMD at the total hip at 12 months
- 3. Percent change from baseline in BMD at the femoral neck at 12 months

P-values for treatment comparisons of all other efficacy endpoints will be generated to support the study findings without any adjustments for multiplicity.

## 3.8 Subgroups

The following subgroups will be created for possible use in selected data analyses. Section 4.2 will describe the specific analyses to be performed for each subgroup.

- Age ( $<65, 65 <75, \ge 75$ )
- Race (White, Black or African-American, Asian, and Other Races [i.e., American Indian or Alaska Native, Native Hawaiian or Other Pacific Islander, Other, and Multiple (more than 1 race category chosen)])
- BMI (< 25, 25 <  $30, \ge 30$ )

- Region (North America including USA and Canada, Europe including Poland and Italy)
- Prior clinical fracture (Yes = Subjects with a record in medical history with "fracture" in the preferred term, No)
- Prevalent vertebral fracture (Yes = Subjects with any vertebral fracture with a score> 0, No)
- Prior fracture (Yes =Subjects with a prevalent vertebral fracture and / or a prior clinical fracture, No)
- Smoking status (current, former, never)
- Lumbar spine BMD T-score at baseline ( $\leq -2.5$ , > -2.5)
- Total hip BMD T-score at baseline ( $\leq -2.5$ , > -2.5)
- Femoral neck BMD T-score at baseline ( $\leq -2.5$ ,  $\geq -2.5$ )
- s-PINP at baseline (tertile values)
- Total testosterone level (<9.36 nmol/L,  $\geq 9.36 \text{ nmol/L}$ )
- Estradiol level ( $\leq$ 73.4 pmol/L, >73.4 pmol/L)

## 3.9 Anti-Abaloparatide Antibody Status

At Day 1, Month 1, Month 3, Month 6, Month 9, Month 12/EOT, and Month 13/EOS, for subjects in the abaloparatide-SC group, the anti-abaloparatide antibody (ADA) assessment in the serum samples for immunogenicity testing will be categorized by two outcomes:

- Negative for the ADA (ADA-)
- Positive for the ADA (ADA+)

For those subjects with a positive ADA (i.e, ADA is present), the serum samples will be further assessed for the presence of neutralizing anti-abaloparatide antibodies (NAb), and the results will be categorized by two outcomes:

- Negative for the NAb (NAb-)
- Positive for the NAb (NAb+)

Subjects' ADA status and presence of NAb by Month 12 (ADA-, ADA+/NAb+, ADA+/NAb-, All ADA+) will be defined as follows:

- Subjects will be classified as ADA- if they were ADA- in all post-baseline immunogenicity assessments during the 12 months treatment period.
- Subjects will be classified as ADA+ and NAb+ if they were ADA+ at any post-baseline immunogenicity assessment and NAb+ at any subsequent tests during the 12 months treatment period.
- Subjects will be classified as ADA+ and NAb- if they were ADA+ at any post-baseline immunogenicity assessment and NAb- at all subsequent tests during the 12 months treatment period.

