#### **Antibody Population**

The antibody population will include those abaloparatide-SC treated subjects in the Safety population who have at least one post-baseline anti-abaloparatide antibody assessment.

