The primary analysis using the PMM with the wash-out imputation method, and the other analyses using the MMRM model and the ANCOVA model using LOCF method, will be repeated using the PP population to support the findings from the ITT population.

For the primary efficacy endpoint using PMM analysis with wash-out imputation, subgroup analyses for each of the subgroups defined in Section 3.8 will be performed. The treatment groups will be compared within each subgroup. A forest plot of the estimated least square (LS) mean differences between the treatment groups (and corresponding 99% CIs) will be presented

by subgroup. Additional exploratory analyses examining subgroup effect and treatment by subgroup interaction may be performed, if warranted.

The efficacy analysis using MMRM model will also be repeated for the Antibody population, in which the subjects who are ADA+ at any post-baseline time point will be compared with subjects who are ADA- at all post-baseline time points. The MMRM model will include the fixed effects of ADA status, DXA instrument manufacturer, visit, and ADA status-by-visit interaction, with the baseline lumbar spine BMD as covariate.

To investigate the effect of the COVID-19 pandemic, the following sensitivity analyses will also be performed:

- a) PMM analysis with wash-out imputation for subjects who completed or withdrew from the study before 01 March 2020 and for subjects who completed or withdrew from the study on or after 01 March 2020. The analysis visit windows described in Table 4 will be used.
- b) PMM analysis with wash-out imputation using the nominal visit.
- c) PMM analysis with wash-out imputation excluding BMD measurements collected outside the allowable time period for data collection. In this analysis, BMD assessments are allocated to a Visit based on the inclusion rules shown in Table 5 below re: Sensitivity Analysis c).
- d) PMM analysis with wash-out imputation excluding BMD measurements which are more than 30 days after the ideal visit day. In this analysis, BMD assessments are allocated to a Visit based on the inclusion rules shown in Table 5 below re: Sensitivity Analysis d).

Visit	Ideal Visit Day	Sensitivity Analysis c): Allowable days from first dose of study drug	Sensitivity Analysis d): Allowable days from first dose of study drug
Month 3	90	2 —120 days	2—120 days
Month 6	180	121—270 days	121—210 days
Month 12	360	271—390 days	271—390 days

 Table 5:

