The duration of study drug exposure, duration category in months ( $\leq 1$  month,  $1 < to \leq 3$  months, 3 to  $\leq 6$  months, 6 to  $\leq 9$  months, and > 9 months), number of doses delivered, and percent compliance to study drug administration will be summarized by treatment group for the Safety, ITT, and PP populations.

To evaluate the relationship between study drug exposure and the antibody status, the duration of study drug exposure and percent compliance to study drug administration will also be summarized by antibody status (ADA-, ADA+/Nab+, ADA+/Nab-, All ADA+, and Overall) using the Antibody Population.

If a subject is shown to be <80% compliant with study drug administration using both calculations of study drug administration compliance, this subject will be considered as having a significant protocol deviation and thus excluded from the Per-Protocol Population.

Subjects' drug exposure and compliance will be carefully reviewed against the onset of the COVID-19 pandemic. Each subject's study drug exposure and compliance prior to 01 March 2020 and on or after 01 March 2020 will be calculated based on information collected from the subject diary:

- For subjects with last dose date prior to 01 March 2020 and subjects with first dose date on or after 01 March 2020, their duration of study drug exposure (days), number of doses delivered, and percent compliance to study drug administration relative to 01 March 2020 will be calculated as above based on missed doses in subject diary.
- For subjects who started taking the study drug prior to 01 March 2020 and continued on or after 01 March 2020, their duration of study drug exposure and compliance before 01 March 2020 and on or after 01 March 2020 will be calculated as follows:
  - Duration of study drug exposure relative to 01 March 2020:
    - Duration before 01 March 2020 = 29 February 2020 date of first dose + 1
    - Duration on or after 01 March 2020 = Overall duration of study drug exposure duration before 01 March 2020; where overall duration of study drug exposure = last dose date – first dose date + 1
  - The number of doses delivered relative to 01 March 2020:

- Number of doses delivered before 01 March 2020 = A {B + ([C x D] / E)}, and will be rounded to the nearest integer; where:
  - A = Duration of study drug exposure before 01 March 2020
  - B = Total number of missed doses from pens dispensed before 01 March 2020 and with scheduled return dates before or on 01 March 2020

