- TEAEs leading to study discontinuation by SOC and PT
- TEAEs leading to death by SOC and PT
- Serious TEAEs by SOC and PT
- Treatment-related serious TEAEs by SOC and PT
- Most common (>=5% in any treatment group) TEAEs by SOC and PT
- Non-TEAEs by SOC and PT

SOCs will be sorted in alphabetical order. Within an SOC, AEs will be sorted in descending order of the total number of subjects with the preferred term in the abaloparatide group.

To explore the relationship between TEAEs and the duration of study drug exposure, the incidence of TEAEs by time of onset ( $\leq 1$  month,  $1 < to \leq 3$  months,  $3 < to \leq 6$  months,  $6 < to \leq 9$  months, and >9 months) will be summarized by treatment group, SOC and PT. Subjects with multiple occurrences of an AE within a time period will be counted once in each time period that an onset of the AE occurs.

To evaluate the relationship between TEAEs and the antibody status, the incidence of TEAEs will be summarized by antibody status (ADA-, ADA+/Nab+, ADA+/Nab-, All ADA+, and Overall), SOC, and PT using the Antibody Population. A summary of TEAEs by PT and antibody status will also be presented, in which TEAEs will be sorted in descending order of total number of subjects with the preferred term in the overall abaloparatide-SC treatment group.

During the COVID-19 pandemic, AEs may be assessed through phone/video by the investigator conducting the study visit with subjects remotely. To explore the effect of the COVID-19 pandemic on reported AEs, summaries of TEAEs by SOC and PT, TEAEs leading to treatment discontinuation, and serious TEAEs will also be presented:

- by subject's study status relative to COVID-19 pandemic onset (subjects who completed or withdrew from the study before 01 March 2020, vs subjects who completed or withdrew from the study on or after 01 March 2020)
- by AE onset dates relative to COVID-19 pandemic onset (AE occurs before 01 March 2020, vs AE occurs on or after 01 March 2020)
- by region (North America and Europe)

The number of subjects with any TEAEs, the number of subjects with any SAEs, and the number of subjects with TEAEs leading to study drug withdrawal will also be summarized by treatment group, SOC, PT and age group (< 65, 65 - < 75, and  $\ge$  75 years). Similar tables will be provided by treatment group, SOC, PT and BMI group (BMI < 25, 25  $\le$  BMI < 30, and BMI  $\ge$  30).

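### Adverse events by antibody status use an ever/never label fixed by later samples, so the ADA+ to ADA- ratio can leave 1 in either direction with no antibody effect

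*SAP*

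**What the plan says.** - **Status (SAP 3.9).** A man is negative only if every treatment-period sample is negative: "Subjects will be classified as ADA- if they were ADA- in all post-baseline immunogenicity assessments during the 12 months treatment period". The positive side needs one sample: "Subjects will be classified as ADA+ and NAb+ if they were ADA+ at any post-baseline immunogenicity assessment", with the neutralizing split resting on later tests. No onset date or minimum follow-up enters.
- **Who is counted (SAP 2.1).** "The antibody population will include those abaloparatide-SC treated subjects in the Safety population who have at least one post-baseline anti-abaloparatide antibody assessment". Men with no post-baseline sample are left out, not labelled ADA-.
- **Where it is used.** In SAP 4.5.3, "the incidence of TEAEs will be summarized by antibody status", and AESIs are treated the same way. SAP 4.5.1 uses it for exposure and compliance ("To evaluate the relationship between study drug exposure and the antibody status"). For lumbar spine BMD, SAP 4.3.1 fits an MMRM in which "the subjects who are ADA+ at any post-baseline time point will be compared with subjects who are ADA- at all post-baseline time points". SAP 4.3.2 repeats this for the key secondary endpoints.
- **Not planned.** There is no time-updated status, landmark, person-time rate by ADA status, or rule that an event must follow first positivity. The TEAE onset-time table in SAP 4.5.3 is by treatment group. The by-visit antibody counts and titres in SAP 4.5.4 are not linked to outcomes.

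**The concern.** The label depends on the future. A man's Month 2 event goes in the ADA+ column if his Month 9 sample turns out positive. To be ADA+ he must also stay on study until he converts, while a man who leaves before converting is ADA-. Antibody effect is therefore mixed with time on study, and some events precede their supposed cause.

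Leaving is tied to the outcomes being compared. Under Protocol 4.3.1, severe hypersensitivity and confirmed BMD loss of at least 7% require withdrawal, and serious AEs allow it. Hypersensitivity is also an AESI category tabulated by antibody status. The tables meant to show whether antibodies relate to safety could suggest harm, mask it or suggest protection, and a reader could not tell which.

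**Working it through.** The plan gives no figure for these comparisons, so there is none to reproduce.

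**From the documents:** 150 men on abaloparatide and drop-out δ = 0.10 (SAP 3.1); a month is 30 days (Protocol 6.2), so 12 months is 360 days; antibody samples at Months 1, 3, 6, 9 and 12 (SAP 4.5.4) and at Early Termination (Protocol 6.2.13).

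**Assumed:** a share p of 20%, 50% or 80% converts; conversion and leaving times are uniform over 12 months unless stated; the event rate is constant; every leaver gives an Early Termination sample; there is no antibody effect unless stated.

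**1. Order of events.** The first post-baseline sample is at Month 1. Every event in roughly the first 30 days precedes any post-baseline antibody result, yet counts under ADA+ if any later sample is positive.

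**2. Random leaving.** A converter who leaves does so before converting with probability 1/2.

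- Share of leavers labelled ADA-: 1 − p/2 = 90%, 75%, 60%.
- Would-be positives labelled ADA-: 150·p·δ/2 = 1.5, 3.75, 6.0 men.
- Mean follow-up, ADA+: 360·[(1−δ) + (δ/2)(2/3)]/(1−δ/2) = 360 × 0.9333/0.95 = 353.7 days.
- Mean follow-up, ADA-: 360·[(1−p)(1−δ/2) + (pδ/2)(1/3)]/[(1−p) + pδ/2]. This is 360 × 0.7633/0.81 = 339.3 days, 360 × 0.4833/0.525 = 331.4 days and 360 × 0.2033/0.24 = 305.0 days.
- For an uncommon event the incidence ratio is close to the follow-up ratio: 353.7/339.3 = 1.04, 353.7/331.4 = 1.07, 353.7/305.0 = 1.16.

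**3. Leaving caused by events.** Take a 12-month event risk R = 0.20, with one third of events leading to leaving and no other leaving. About half of converters' events fall before conversion, so a = (1/3)(0.20)/2 = 0.0333 of converters leave with an event and are labelled ADA-.

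- Incidence, ADA+: (R−a)/(1−a) = 0.1667/0.9667 = 17.2%.
- Incidence, ADA-: [(1−p)R + pa]/[(1−p) + pa] = 20.7%, 22.6%, 29.4%.
- Ratio: 0.83, 0.76, 0.59.

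**4. Simulation** over p from 20% to 80%, with early, uniform or late conversion, agrees:

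| No true antibody effect | Ever/never incidence ratio | Rate ratio, split at first positive sample |
|---|---|---|
| 10% random drop-out | 1.02 to 1.19 | 0.99 to 1.01 |
| One third of events lead to leaving | 0.57 to 0.97 | 0.99 to 1.03 |

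The share of ADA+ men's first events that precede conversion (random drop-out) is about 15% with early, 51–57% with uniform and 66% with late conversion.

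**5. A real effect.** With a true rate ratio of 2 after conversion, 10% event risk and uniform conversion, the ever/never ratio is 1.50 to 1.71 and the split gives about 1.8 to 1.9. About half of a converter's follow-up precedes conversion, so his average rate is only (1+2)/2 = 1.5 times baseline. The split falls short of 2 because conversion is seen only at visits.

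**6. A condition on the split.** It is neutral only if the event rate is steady over time. Suppose instead the rate is 0.25 in Month 1 and 0.04 per month afterwards. Take two men followed for 12 months, one first positive at Month 6 and one never positive, and count all events. ADA- time has (0.25 + 5×0.04) + (0.25 + 11×0.04) = 1.14 events in 18 months, or 0.063 per month. ADA+ time has 0.04 per month. The crude ratio is 0.63 with no antibody effect. Within any interval after Month 1 it is 0.04/0.04 = 1.

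**7. BMD.** In the Month 12 contrast, bias is within 0.03 percentage points under random leaving and about zero with early conversion. If men with poor Month 3 BMD leave more often (about 18% leave in all), it is +0.44 to +0.93 points with uniform and +0.61 to +1.19 with late conversion, favouring ADA+.

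**The case against.** The strongest reply is that little is lost. The AE and exposure tables are descriptive, exposure is shown for the same antibody groups so unequal follow-up is visible, and antibody and AE listings let timing be checked man by man. SAP 3.2 reports the antibody analyses separately, and SAP 3.7 leaves them out of the fixed sequence. All of that stands and limits the consequence. But listings and a visible exposure gap do not correct a table, and no planned table puts events in order relative to conversion.

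Three stronger readings are tempting, and the documents do not support them:

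- *All early leavers are labelled ADA-.* Men already positive stay ADA+, men without a post-baseline sample are excluded, and leavers are encouraged to attend Early Termination, which includes an antibody sample.
- *The bias has a known size and direction, for instance most TEAEs in ADA+ men precede conversion.* Direction depends on why men leave, and the pre-conversion share on when they convert. The documents give no conversion or event rate.
- *A hazard ratio of 2 that shows as a risk ratio near 1.3 measures the damage.* That sets two scales side by side. With 48% risk in ADA- men, a hazard doubled from day one and perfectly classified gives 1 − 0.52² = 73%, a risk ratio of only 0.73/0.48 = 1.52.

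**Conclusion.** The point holds in limited form. The ever/never label puts events before first positivity under ADA+ and men who leave before converting under ADA-. With no antibody effect, the TEAE ratio can move modestly above 1 (to about 1.19) with the planned 10% drop-out at random, or well below 1 (to about 0.57) if a third of events lead to leaving. These ranges rest on assumed conversion shares and timing, a constant event rate and full Early Termination sampling. BMD bias matters only if poor responders leave and conversion is not early. A reader might infer that the primary or key secondary claims are affected; they are not. The change is worth making because a better table can be built from dates already collected.

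**What to change.** - **SAP 4.5.3:** keep the ever/never tables and add TEAE and AESI tables by time-updated status. Events and person-time before the first ADA+ sample count as ADA-, and those from it onward as ADA+. Show exposure-adjusted rates overall and by AESI category, not for every SOC and PT. Because early events may be more frequent, show the rates within the onset windows that SAP 4.5.3 already uses, or adjust for time since first dose.
- **SAP 4.5.1:** state that exposure by antibody status is affected by time on study and is not evidence of an antibody effect.
- **SAP 4.3.1 and 4.3.2:** a Month 6 landmark for BMD is optional. It drops men who left before Month 6 and labels later converters ADA-.
- **Reconcile the period.** SAP 3.9 limits status to the 12-month treatment period, whereas the BMD comparison in SAP 4.3.1 and 4.3.2 uses all post-baseline time points, which could admit the Month 13 sample.

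**Cost:** SAP wording and a few tables; no new data. The first positive sample can trail conversion by up to about 3 months, so some post-conversion events will still count as ADA-. Counts by ADA and NAb group will be sparse with about 150 men.
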